9.4.2.7. Bioequivalence Criteria

Based on the statistical results of 90% confidence interval for the ratio of the geometric least square means for both ln-transformed pharmacokinetic parameters Cmax and AUC(0-t), conclusion will be drawn for Test Study Intervention-T vs. Reference Study Intervention-R for albendazole with following considerations.

For Cmax and AUC(0-t):

- 1. If within-reference intra-subject CV of ln-transformed Cmax and/or AUC(0-t) ≤ 30% then bioequivalence of the test study intervention with that of the reference study intervention will be concluded, if the 90% confidence interval falls within the acceptance range of 80.00–125.00% for ln-transformed pharmacokinetic parameter Cmax and AUC(0-t).
- 2. If within-reference intra-subject CV of ln-transformed Cmax and/or AUC(0-t) > 30% then Cmax and/or AUC(0-t) limit will be widened using scaled-average-bioequivalence. Under scaled-average-bioequivalence, [U,L] = exp [±k·swR] where U is the upper limit of the acceptance range, L is the lower limit of the acceptance range, k is the regulatory constant set to 0.760 and SwR is the within-subject standard deviation of the ln transformed values of Cmax and/or AUC(0-t) of the reference study intervention.
- 3. If within-reference intra-subject CV of ln-transformed Cmax and/or AUC(0-t) ≥ 50% then Cmax and/or AUC(0-t) bioequivalence limits will be widened to a maximum of 69.84 143.19%.

Bioequivalence of the test study intervention with that of the reference study intervention will be concluded for Cmax and/or AUC(0-t), if both of the following conditions are satisfied:

- The 90% confidence interval for ln-transformed data of Cmax and/or AUC(0-t) falls within the newly widen range [U, L] = $\exp[\pm k \cdot s_{WR}]$, which is based upon the within-subject variability observed for Cmax.
- The geometric least square mean ratio (GMR) of test to reference for Cmax and/or AUC(0-t) falls within the acceptance range of 80.00–125.00%.

Data of metabolite albendazole sulfoxide will be provided as supportive information only.

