10.1.9. Source documents

- All clinical raw data generated during conduct of the study will be directly entered in the respective electronic source forms / eCRF. Electronic software (BizNET, IMPTrack etc.) will be used for capturing the data generated during conduct of the study as per in-house SOPs. The study specific activity such as study intervention administration, sample collection, meal distributions, vitals and clinical examination etc. will be directly entered into electronic source forms/eCRF. However, the activity like such as participant's consent, duty delegations records etc. will be available in paper copy (wet ink signature).
- All source data and transcribed data forms will be compiled by the study personnel
 assisting in the study and will be checked wherever applicable for completeness.
 Further, information of Type and location of data generated for study will be traceable
 from Trial Master File.
- All bio-analytical raw data of sample processing and associated data such as solution
 preparation, role allocation etc. will be directly entered in the respective source data
 forms. The data acquisition system software will be used for the quantitative
 determination and Biolyte software will be used for review of generated data as per inhouse SOPs. All data related to the project will be in the custody of the designated
 study personnel until transferred to archives.
- Once the concentration data is received from bio-analytical department through Biolyte software, data will be combined with randomization schedule and actual sampling time point, as applicable. Handling of the concentration data and pharmacokinetic and statistical analysis will be done as per in-house SOPs. All pharmacokinetic and statistical analysis will be performed on network drive. Archival of the pharmacokinetic and statistical data will be done as per defined archival procedure.
- A paper source/forms (if required to be used due to temporary non-functioning of software or no provision to document in software) will be maintained and filed with project specific binders as per in-house SOPs.

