5.1 Pharmacokinetic analysis

Pharmacokinetic analysis will be performed on the available concentration data of all the participants.

Criteria for exclusion of pharmacokinetic parameters of particular participants from statistical analysis will be as below:

Participants who were discontinued/withdrawn and do not have evaluable data for at least 1 treatment and 1 reference drug period will be excluded.

Day 2: Subsequent day after study intervention administration in each period.

Three consecutive missing (M) / Non-Reportable (NR) samples in elimination phase may significantly influence the AUC(0-t) and elimination phase dependent parameters (AUC0- ∞ , AUC0-t, t1/2, λz , AUC_%Extrap_obs). Inclusion of such parameters in the statistical analysis may mislead the final outcome. Hence, AUC(0-t) and elimination phase dependent parameters (AUC0- ∞ , AUC(0-t), t1/2, λz , AUC %Extrap obs) will be excluded.

The concentration—time profiles of subjects who exhibit pre-dose concentrations higher than 5% of the corresponding Cmax of that period will be excluded from the statistical analysis [Note: a statistical sensitivity analysis including the same will be provided for information purpose].

Participants without measurable concentrations or who have only very low plasma concentrations relative to that of the product in question, will be excluded from the pharmacokinetic and statistical analyses. A participant is considered to have very low plasma concentrations if their AUC is less than 5% of the geometric mean AUC of the product in question, calculated without inclusion of data from the outlying participant [Note: statistical analysis with including the same will be provided for information purpose].

Note: This exclusion will be period specific.

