6.3.2.7 Intercurrent event and handling of missing data

The data will be affected by occurrence of the intercurrent event and only data available while the participant is receiving the treatment will be used under while-on treatment policy strategy. Participant level missing data will not be imputed, and available data will be used in the analysis.

In the case of emesis/vomiting or use of prohibited/rescue medication, the data for that period will not be used for the analysis of PK parameters relating to the primary endpoint using hypothetical strategy.

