6.3.2.8 Bioequivalence criteria

Based on the statistical results of 90% confidence interval for the ratio of the geometric least square means for both ln-transformed pharmacokinetic parameters Cmax and AUC(0-t), conclusion will be drawn for Test Study Intervention-T vs. Reference Study Intervention-R for albendazole with following considerations.

For Cmax and AUC(0-t):

- 1. If within-reference intra-subject CV of ln-transformed Cmax and/or AUC(0-t) \leq 30% then bioequivalence of the test study intervention with that of the reference study intervention will be concluded, if the 90% confidence interval falls within the acceptance range of 80.00–125.00% for ln-transformed pharmacokinetic parameter Cmax and AUC(0-t).
- 2. If within-reference intra-subject CV of ln-transformed Cmax and/or AUC(0-t) > 30% then Cmax and/or AUC(0-t) limit will be widened using scaled-average-bioequivalence. Under scaled-average-bioequivalence, [U,L] = exp [$\pm k \cdot _{SWR}$] where U is the upper limit of the acceptance range, L is the lower limit of the acceptance range, k is the regulatory constant set to 0.760 and S_{WR} is the within-subject standard deviation of the ln transformed values of Cmax and/or AUC(0-t) of the reference study intervention.
- 3. If within-reference intra-subject CV of ln-transformed Cmax and/or AUC(0-t) \geq 50% then Cmax and/or AUC(0-t) bioequivalence limits will be widened to a maximum of 69.84 143.19%.

Bioequivalence of the test study intervention with that of the reference study intervention will be concluded for Cmax and AUC(0-t), if both of the following conditions are satisfied:

- The 90% confidence interval for ln-transformed data of Cmax and AUC(0-t) falls within the respective newly widen range [U, L] = $\exp\left[\pm k \cdot _{SWR}\right]$, which is based upon the within-subject variability observed for respective pharmacokinetic parameter.
- The geometric least square mean ratio (GMR) of test to reference for Cmax and AUC(0-t) falls within the acceptance range of 80.00–125.00%.

Data of metabolite albendazole sulfoxide will be provided as supportive information only.

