CV%		XX.X	XX.X	XX.X	XX.X	XX.X	XX.X	XX.X	XX.X		
Geometric	Geometric Mean		XX.XXX	XX.XXX	XX.XXX	xx.xxx	XX.XXX	XX.XXX	XX.XXX		
95% CI of geon	netric mean	x.xxx-	x.xxx-	x.xxx-	x.xxx-	x.xxx-	x.xxx-	x.xxx-	X.XXX-X.XXX		
7570 CI 01 gcon	ileti ie ilieali	X.XXX	X.XXX	X.XXX	X.XXX	X.XXX	X.XXX	X.XXX			

<Note: Repeat the same table as 14.2.2.3 for albendazole sulfoxide >

14.2.1.4 Pharmacokinetic parameters (untransformed) of data excluded from statistical analysis for albendazole (if applicable)

Lambda Therapeutic Research Ltd.

Project No. 0110-23

Table No. 14.2.1.4

Confidential

Pharmacokinetic parameters (untransformed) of data excluded from statistical analysis for albendazole

Participants	Period	Sequence	Formulation	Tmax (unit)	Cmax (unit)	AUC0-t (unit)	AUC0-inf (unit)	AUC_%Extrap_obs (%)	Lambda_z (unit)	t1/2 (unit)
1001				XX.XXX	XX.XXX	xx.xxx	XX.XXX	xx.xxx	xx.xxx	xx.xx
1002				xx.xxx	xx.xxx	xx.xxx	XX.XXX	XX.XXX	xx.xxx	xx.xx
						•				
						•	•		•	
						•	•	•	•	
								•		
n				xx.xxx	xx.xxx	xx.xxx	XX.XXX	xx.xxx	xx.xxx	xx.xx

<Note: Repeat the same table as 14.2.2.4 for albendazole sulfoxide.>

14.2.1.5 Pharmacokinetic parameters (In-transformed) of albendazole for Test Product-T and Reference Product-R

Lambda Therapeutic Research Ltd.

Confidential

Project No. 0110-23

Table No. 14.2.1.5

Pharmacokinetic parameters (In-transformed) of albendazole for Test Product-T and Reference Product-R

		Cma	ax	Α	AUC0-t	
Participants	Sequence	Formul	ation	Formulation		
		T	R	T	R	
1001		XX.XXX	XX.XXX	XX.XXX	XX.XXX	
1002		XX.XXX	XX.XXX	XX.XXX	XX.XXX	
n		XX.XXX	XX.XXX	XX.XXX	XX.XXX	
N		XX	XX	XX	XX	
Mean	ı	XX.XXX	XX.XXX	XX.XXX	XX.XXX	
95% CI of arithr	netic mean	X.XXX-X.XXX	x.xxx-x.xxx	x.xxx-x.xxx	X.XXX-X.XXX	
SD		XX.XXXX	XX.XXXX	XX.XXXX	XX.XXXX	
Min		XX.XXX	XX.XXX	XX.XXX	XX.XXX	
Media	n	XX.XXX	XX.XXX	XX.XXX	XX.XXX	
Max		XX.XXX	XX.XXX	XX.XXX	XX.XXX	
CV%		XX.X	XX.X	XX.X	XX.X	
Geometric M	ean	XX.XXX	XX.XXX	XX.XXX	XX.XXX	
95% CI of geom	netric mean	X.XXX-X.XXX	X.XXX-X.XXX	X.XXX-X.XXX	X.XXX-X.XXX	

<Note: Repeat the same table as 14.2.2.5 for albendazole sulfoxide.>

14.2.1.6 Individual Pharmacokinetic parameter (In-transformed) of albendazole for Test Product-T1 (first administration), Test Product-T2 (second administration), Reference Product-R1 (first administration) and Reference Product-R2 (second administration)

Lambda Therapeutic Research Ltd.

Confidential

Project No. 0110-23

Table No. 14.2.1.6

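### The 5% low-exposure exclusion asks for no cause, so very low profiles confined to the test product are removed before the bioequivalence decision; a narrow, cheap safeguard would close this gap

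*SAP*

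**What the plan says.** SAP 5.1 and protocol 8.5 carry the same rule. Data are excluded from the pharmacokinetic and statistical analyses "if their AUC is less than 5% of the geometric mean AUC of the product in question", with that mean computed without the outlying participant. The rule covers test and reference alike, and the numerical threshold is its only trigger. The SAP adds "Note: This exclusion will be period specific"; the protocol does not.

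On the analysis that keeps these profiles, SAP 5.1 says only that "statistical analysis with including the same will be provided for information purpose".

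SAP 6.3.2.8 states that bioequivalence "will be concluded for Cmax and AUC(0-t), if both of the following conditions are satisfied"; the corresponding sentence in protocol 9.4.2.7 reads "will be concluded for Cmax and/or AUC(0-t), if both of the following conditions are satisfied". The two conditions are the 90% CI within the scaled limits and the GMR within 80.00-125.00%. Neither section mentions the inclusive analysis.

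Vomiting and interfering medication have a separate rule in SAP 6.3.2.7: "In the case of emesis/vomiting or use of prohibited/rescue medication, the data for that period will not be used for the analysis".

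Deleted data are reported. Shell 14.2.1.4 is titled "Pharmacokinetic parameters (untransformed) of data excluded from statistical analysis for albendazole", shell 14.2.1.11 gives the concentrations, and listing 16.2.3.1 has a reason column.

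**The concern.** Vomiting and prohibited medication are already dealt with, so the 5% rule mainly catches low profiles that those events do not explain. Such profiles could include a tablet that failed to release its drug. The study exists to show that tablets from a new manufacturing site match those from the old one (protocol 4.2), so a cluster of very low profiles on the test product alone would be informative. As written, the cluster is deleted, the verdict rests on the remaining profiles, and nothing says what is concluded if the inclusive analysis disagrees.

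The effect depends on where the low profiles fall:

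- None: no effect.
- Reference only, true ratio low: deletion protects, because kept low reference profiles raise T/R and widen the scaled limits.
- Test only, ratio otherwise at or below about 1: deletion can turn a fail into a pass.
- Test only, ratio well above 1: the effect reverses slightly.

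The third case is the concern.

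**Working it through.** **Inputs from the documents.** 48 evaluable participants (96 test and 96 reference profiles), CV 48%, T/R 0.90-1.11 (protocol 9.6, SAP 3.3). The limits are exp(±0.760·s_WR), capped at 69.84-143.19%, with the GMR within 80-125% (SAP 6.3.2.8). **Assumed:** number of low profiles; depth 3% of normal; between-subject SD 0.8.

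**1. The plan's own figure.** Stated joint power at CV 48% with 48 completers is 90.3% (1,000 replicates, SE √(0.903×0.097/1000) = 0.94 points). Simulating the SAP 6.3.2.8 rule for both endpoints gives 92.5-92.6%; a linearised scaled criterion with k = 0.760 gives 91.5%. This is close enough to compare one exclusion rule with another. The 93.7% in the high-CV column was not reproduced (85-86%). That is a separate matter, and the main case here uses CV 48%.

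**2. Shift in the ratio.** Each test profile kept at 3% multiplies the estimated GMR by 0.03^(1/96) = 0.964. Two give 0.930 and three give 0.896. From 0.90 the GMR becomes 0.868, 0.837 and 0.806. Deletion returns it to 0.90.

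**3. The limits do not compensate.** σ_w² = ln(1 + 0.48²) = 0.207, so σ_w = 0.455 and the limits are exp(±0.760×0.455) = 0.708 to 1.413. s_WR uses reference profiles only. Test failures therefore lower the GMR and widen the CI but leave the limits where they were.

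**4. Pass rates, test-only low profiles** (one endpoint, 24 TRTR + 24 RTRT; fixed subject, period and formulation effects; 1,000-2,000 runs per case, SE at most 1.6 points; ranges span repeat simulations):

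| T/R in other profiles | 1 kept | 2 kept | 3 kept | Deleted |
|---|---|---|---|---|
| 0.90 | 81-83% | 59-61% | 32-36% | 93-95% |
| 0.95 | 96% | 84% | 63% | 99% |
| 1.00 | 99.4% | 95-95.5% | 85-86% | 99.8-100% |
| 1.11 | 98-99% | 98-99% | 98-99% | 95% |

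With no low profile at T/R 0.90 the rate is 95.7%. At CV 62% and T/R 0.90 the kept rates are 80%, 59% and 35%, against 90-92% deleted. Varying depth from 1% to 4.5% (T/R 0.90, three failures) gives 9% to 44% kept, against 94% deleted. A joint Cmax/AUC simulation at 4% depth agrees: two failures at T/R 0.90 give 57.8% kept and 92-93% deleted.

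**5. Reference side.** At true GMR 0.80, two low reference profiles give 84% passing if kept and 45% if deleted.

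**6. Chance alone.** If the AUC variance 0.814 in protocol Table 10 is the total log-variance, p = Φ(ln 0.05/√0.814) = 0.00045 per profile. If it is between-subject only, adding 0.207 gives Φ(ln 0.05/√1.021) = 0.0015. Over 96 test profiles treated as independent, at least one is low in 4.2% or 13.6% of studies, and two or more in 0.09% or 0.95%. With a within-subject CV of 62% added instead, p = 0.0025 and at least one is low in 1 − (1 − 0.0025)^96 = 21%.

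**The case against.** The strongest reply is that the rule was fixed in advance, treats both products alike, promises an inclusive analysis, and lists every deleted value with its reason. An assessor would see a cluster. All of that stands. A reader might infer that the rule is one-sided or hides test failures; the documents do not support that. What disclosure does not settle is what a conflict between the two analyses does to the verdict.

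The effect is also hypothetical. No failure rate is given, protocol Table 6 shows only minor product differences, and chance seldom triggers the rule. The 32% figure needs three test-only failures together with T/R at the edge of the planned range. This limits the weight of the point but does not remove the case.

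A reader might go further and make the inclusive analysis the sole primary one, or require both analyses to pass whenever any low profile is removed. The first would lose the reference-side protection in step 5. The second is costly: with three reference-only low profiles at T/R 1.11, within the plan's own range, about 45% would pass against 95% now.

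The trial is open label, so recording of causes is not blind to product. The safeguard is timing: a cause recorded before concentrations exist cannot be prompted by a low result. Under protocol 10.1.9, only once concentrations are received does the sentence "data will be combined with randomization schedule and actual sampling time point, as applicable" apply.

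A reader might also think a profile with nothing measurable, having no logarithm, makes the inclusive analysis unworkable. SAP 6.3.2.7 does not impute missing participant-level data, so such a profile most naturally contributes no value. A sentence saying so is a clarification only.

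**Conclusion.** The point holds in a narrow form and is a cheap improvement, not a flaw that undermines the design. If very low profiles occur on the test product only and T/R is otherwise at or below about 1, the plan deletes them before the decision, and a failing study can pass. With 48 completers, CV 48%, 3% depth and T/R 0.90, the pass rate with one, two or three such profiles is about 81%, 59% and 32% if they are kept, against 93-95% under the plan. At T/R 1.00 one or two matter little; well above 1 the effect reverses slightly. Counts and depth are assumptions. The documents do not support a claim that such failures are expected, or that a false pass is likely.

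**What to change.** In SAP 5.1 and 6.3.2.8 and protocol 8.5 and 9.4.2.7, keep the symmetric 5% rule and add:

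- Where it removes at least one measurable test profile without a documented non-product cause recorded before concentrations are available, bioequivalence is concluded only if the criteria are met both with and without the low profiles.
- Where only reference profiles are removed, the current rule applies unchanged.

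Clarifications only: state how a profile with no measurable concentration is handled, align protocol 8.5 with the SAP's period-specific note and list that note in SAP section 8, and name the output for the inclusive analysis.

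**Cost.** Wording in four sections and one named output; nothing changes if no low test profile occurs. If low profiles are unrelated to product and fall on both, the pass rate at T/R 0.90 is about 94% against 95% now with one per product, and 90% against 94% with two per product. At T/R 1.00 it is 99.6% or more either way.

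The loss is larger when chance puts low profiles on test only: 95 − 83 = 12 points for one and 95 − 61 = 34 for two at T/R 0.90. Weighted by step 6, with exactly one low profile in 4.1% or 12.65% of studies, the average cost is 0.041×12 + 0.0009×34 = 0.5 points, up to 0.1265×12 + 0.0095×34 = 1.8 points. The change should be made before concentrations are seen; a rule for discordant results chosen afterwards would be open to challenge.

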5.2 Pharmacokinetic Parameters

The following pharmacokinetic parameters will be computed for albendazole and albendazole sulfoxide using non-compartmental model of Phoenix[®] WinNonlin[®] Version 8.3 or higher (Certara L.P.) for each period:

• Primary Pharmacokinetic Parameters: Cmax, AUC_{0-t}

• Secondary Pharmacokinetic Parameters: AUC_{0-∞}, Tmax, λz, t1/2, AUC %Extrap obs

Primary PK Paran	net	ers:
Cmax	:	Maximum measured plasma concentration.
AUC(0-t)	••	Area under the plasma concentration versus time curve from time zero to the last measurable concentration as calculated by linear trapezoidal method.
Secondary PK Par	am	neters
AUC0-∞	:	Area under the plasma concentration versus time curve from time zero to time infinity. Where $AUC0-\infty = AUC(0-t) + Ct/\lambda z$, Ct is the last measurable concentration and λz is the terminal rate constant.
Tmax	:	Time of the maximum measured plasma concentration.
λz	:	First order rate constant associated with the terminal (log-linear) portion of the curve. This is estimated via linear regression of time vs. log concentration. This parameter will be calculated by linear least squares regression analysis using at least last 3 non-zero plasma concentration values.
t1/2	:	The terminal half-life will be calculated as 0.693/λz.
AUC_%Extrap_obs	:	The residual area in percentage will be determined by the formula, $[(AUC0-\infty - AUC0-t)/AUC0-\infty] \times 100$.

For all the above computations, actual time points of the sample collection will be used.

Non-quantifiable (NQ) data, such as concentrations below the quantification limit may be excluded or omitted, depending on where they are located in time, see Section 6.3.2.6.

No value of λ_z , AUC_{0-∞}, AUC_%Extrap_obs and $t_{1/2}$ will be reported for cases that do not exhibit a terminal log-linear phase in the concentration versus time profile.

6 Statistical Considerations

6.1 Statistical Hypotheses

According to WHO product specific guidance (Notes on the Design of Bioequivalence Study: Albendazole; 29 March 2021), albendazole pharmacokinetics in the fed state is highly variable (up to 68% for Cmax and 62% for AUC). Therefore, this study was designed as a replicate cross-over study, to estimate variability more accurately and, if indicated, to widen the acceptance range for Cmax and AUC(0-t) (Error! Reference source not found., 2021). Considering the same, full replicate study has been planned in line with WHO product specific guidance document and reference-scaled average bioequivalence approach will be used for hypothesis testing.

The null hypothesis to be tested is:

$$H_0: \frac{\left(\mu_T - \mu_R\right)^2}{\sigma_{WR}^2} \ge \ \theta$$

Versus alternative hypothesis

$$H_1: \frac{\left(\mu_T - \mu_R\right)^2}{\sigma_{WR}^2} < \theta$$

Where: μ_T and μ_R are the means of ln-transformed PK parameters (Cmax and/or AUC) obtained from the BE study for the test and reference products, respectively.

 σ_{WR} is the within-subject standard deviation of the ln-transformed values of PK parameter of the reference study intervention.

Testing will be performed at a level of 0.05 and θ is the scaled average BE limit.

The test drug must pass for primary endpoint PK parameters (Cmax and AUC(0-t)) to demonstrate BE to the reference drug. Let σ_{W0} be the regulatory constant (based on 0.80-1.25 geometric mean ratio restriction criteria) and assumed to be 0.294.

a. The 90% confidence interval of GMR of T/R must be contained within [U, L] = exp [$\pm k \cdot s_{WR}$], which is scale acceptance limit based on k(θS),

Where $k = \ln(1.25)/\sigma_{W0}$ which is approx. 0.760

U is the upper limit of the acceptance range, L is the lower limit of the acceptance range, s_{WR} is the within-subject standard deviation of the ln-transformed values of PK parameter of the reference study intervention.

b. Point estimate of GMR of T/R should be between 80.00 –125.00%.

For the parameters Cmax and AUC(0-t), if the intra-subject CV_W of for the reference study intervention is less than or equal to 0.30 upon trial completion for any of these treatment group, conventional average BE approach with TOST procedure with α =0.05 for each one-sided test will

Albendazole Tablets IP 400 mg

be used to test $0.8 \le GMR \le 1.25$. This is equivalent to requiring that a 90% interval for the true ratio of test to reference geometric means falls entirely within the range of 80.00 to 125.00%. If the intra-subject coefficient of variation (CV_W) of for the reference study intervention is greater than 0.30 upon trial completion, a reference-scaled average bioequivalence approach will be used³.

If the intra-subject variability for Cmax and AUC(0-t) following replicate administrations of the comparator product is > 30%, the acceptance criteria for Cmax and AUC(0-t) will be widened to a maximum of 69.84–143.19%.

